10.3. Clinical Laboratory Tests

Clinical laboratory tests will include serum chemistry and urine pregnancy tests. Descriptive summaries (mean, SD, median, minimum, and maximum) of actual values and changes from baseline will be calculated for each laboratory value for each of the scheduled visits. Shift tables will also be presented.

10.4. ECG

Descriptive summaries (mean, SD, median, minimum, and maximum) of actual values and changes from Baseline will be calculated for each ECG parameter.

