#### **12.4.7. Electrocardiogram Values**

Descriptive summaries (mean, SD, median, minimum, and maximum) of actual values and changes from Baseline will be calculated for each ECG parameter.

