6.3.3. Electrocardiogram (ECG)

A 12-lead ECG is conducted after the subject has been resting (supine) for at least 2 minutes. At a minimum, the following parameters should be collected; PR interval, QRS duration, and QTcF.

The date and time of last dose prior to each ECG is recorded.

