10. SAFETY AND TOLERABILITY

Safety analyses will be performed for the Safety population. Safety evaluations will be based on the incidence, severity, relatedness, and type of adverse events, as well as on clinically significant changes in the subject's ECGs, vital signs, clinical labs, and C-SSRS.

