10.5. Vital Signs

Descriptive summaries (mean, SD, median, minimum, and maximum) of actual values and changes from baseline will be calculated for systolic blood pressure, diastolic blood pressure, heart rate, respiratory rate, oral body temperature, and weight. Changes in weight will be further presented by the percentage of subjects with a 7-10%, >10% to 15%, and $\geq 15\%$ weight change from baseline over time.

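### SAP Section 10 bases safety partly on clinically significant ECG and vital-sign changes, but no planned ECG or vital-sign table counts subjects with such a change in QTcF, blood pressure or heart rate

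*SAP*

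**What the plan says.** SAP Section 10 names two bases for the safety evaluation. The first is adverse events, by incidence, severity, relatedness and type. The second, added to the first, is "clinically significant changes in the subject's ECGs, vital signs, clinical labs, and C-SSRS".

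The subsections then set out what will be produced:

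- **ECG (SAP 10.4):** "Descriptive summaries (mean, SD, median, minimum, and maximum) of actual values and changes from Baseline will be calculated for each ECG parameter". SAP 6.3.3 gives the minimum content of each ECG: "the following parameters should be collected; PR interval, QRS duration, and QTcF".
- **Vital signs (SAP 10.5):** the same five statistics "will be calculated for systolic blood pressure, diastolic blood pressure, heart rate, respiratory rate, oral body temperature, and weight". One item is added, for weight only: "Changes in weight will be further presented by the percentage of subjects with a 7-10" per cent change, followed by two higher bands.
- **Laboratory tests (SAP 10.3):** the same statistics, and then "Shift tables will also be presented".

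The protocol adds no categorical analysis. Its Section 12.4.7 says that summaries of actual values and "changes from Baseline will be calculated for each ECG parameter", and Section 12.4.5 does the same for vital signs. Protocol 12.1.2 lists change over time in blood pressure and heart rate, and in ECG findings, among the secondary safety endpoints. The primary objective in both documents is long-term safety.

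**The concern.** The stated basis of the evaluation is a property of individual subjects: whether a subject had a clinically significant change. The planned ECG, blood-pressure and heart-rate output describes the distribution across subjects. Neither document says what makes a change in these measures clinically significant, and no ECG or vital-sign table counts the subjects who had one.

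The SAP goes further elsewhere. It adds shift tables for laboratory values and percentage-of-subjects bands for weight, and gives no reason for stopping short on the other measures.

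At stake is whether the report of a long-term safety study can say how many subjects had a marked QTcF, blood-pressure or heart-rate change at any time on treatment. If no criterion is set in advance, any such count would have to use limits chosen after the data are seen.

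**Working it through.** **Step 1. Match each measure to its planned output.**

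| Measure | Five summary statistics | Planned table that classifies subjects |
|---|---|---|
| ECG parameters (SAP 10.4; protocol 12.4.7) | yes | none |
| Blood pressure, heart rate (SAP 10.5; protocol 12.4.5) | yes | none |
| Weight (SAP 10.5) | yes | bands of percentage change |
| Laboratory values (SAP 10.3) | yes | shift tables |

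**Step 2. Is there a figure in the plan to reproduce?** No. The documents give about 150 subjects with no inputs behind that number, and no limit for QTcF, blood pressure or heart rate. Everything below is illustration under assumed values.

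**Step 3. How far do several large changes move the mean?** Assume that k of n subjects rise by 60 ms and the rest average no change.

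Shift in mean = k × 60 / n. With n = 150:

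- k = 3 (2.0%): 3 × 60/150 = 1.2 ms
- k = 5 (3.3%): 5 × 60/150 = 2.0 ms
- k = 8 (5.3%): 8 × 60/150 = 3.2 ms

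The shift depends only on the proportion k/n. The same proportion in a smaller group gives the same shift. The maximum change shows one value, whatever k is.

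**Step 4. Can the five statistics together recover the count?** Take two constructed sets of 150 changes. The line at +30 is arbitrary and is not a proposed limit.

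- Set A: one each at +65 and −65, ten each at +31 and −31, and 128 at 0. Sum of squares = 2 × 65² + 20 × 31² = 8,450 + 19,220 = 27,670.
- Set B: one each at +65 and −65, sixty each at +12.66 and −12.66, and 28 at 0. The value is √(19,220/120) = 12.66, chosen so that the sum of squares is again 27,670.

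| | Mean | SD = √(27,670/149) | Median | Min | Max | Subjects above +30 |
|---|---|---|---|---|---|---|
| Set A | 0 | 13.63 | 0 | −65 | +65 | 11 |
| Set B | 0 | 13.63 | 0 | −65 | +65 | 1 |

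All five planned statistics agree, yet the counts are 11 and 1. The count cannot be derived from the planned output.

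**Step 5. Would a count be informative at this size?** With n = 150 and a true rate p, P(at least one case) = 1 − (1 − p)^150. This is 77.9% at p = 1%, 95.2% at 2% and 99.95% at 5%. If no subject met the criterion, the one-sided 95% upper bound on the rate would be 1 − 0.05^(1/150) = 1.98%. These figures assume that all 150 subjects are evaluable.

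**The case against.** **Significant changes become adverse events.** Protocol 10.1.1 counts an unfavorable, unintended sign as an adverse event, and protocol 10.2.1 extends this to relevant observations made at visits. SAP 10.2 then counts subjects by preferred term. This stands in part, so a reader should not infer that the number is never produced in any form: a change that the investigator reports is counted. The route still rests on separate judgements at about 25 sites without a common criterion. The documents have a specific reporting rule for clinically relevant laboratory changes (protocol 9.3.3.2.3) and for significant physical findings (SAP 6.2), but only the general sentences for ECG and vital signs. SAP Section 10 also names adverse events and significant changes as separate bases.

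**Individual values are listed.** SAP 7.1 provides for this. Listings give no count and apply no criterion.

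**Section 10 is an introductory sentence, and the endpoints are changes over time.** This stands. Section 10 promises no particular table, and summaries of change do address the protocol 12.1.2 endpoints. A reader might infer that an endpoint goes unanalysed, and the documents do not support that. What is missing is a definition and a supplementary table.

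**One extreme subject would be visible.** This also stands. A single subject with a 60 ms rise moves the mean by only 60/150 = 0.4 ms, but would appear as the maximum change if it were the largest. The loss of information concerns several subjects, not one.

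**Conclusion.** The concern holds in limited form. Carried out as written, the plan yields no ECG, blood-pressure or heart-rate table showing how many subjects had a clinically significant change, although SAP Section 10 makes such changes a basis of the safety evaluation.

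It would be too strong to say that only means and ranges are planned for vital signs. SD and median are included, and weight has bands. The gap is confined to the ECG parameters, blood pressure and heart rate.

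The size can only be illustrated. A 60 ms rise in 2.0% to 5.3% of 150 subjects moves the mean by 1.2 to 3.2 ms, assuming no average change in the rest and all 150 measured. That last condition is unlikely at the later visits of a 15-month study. The conclusion does not depend on these values: Step 4 shows that the five planned statistics do not determine the count.

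This does not invalidate the study. It is an inexpensive improvement to the analysis of the primary objective and should be made.

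**What to change.** Amend SAP 10.4 and 10.5 before database lock:

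1. State the sponsor's own analysis criteria for a clinically significant value, and for a clinically significant change from baseline, in QTcF, systolic pressure, diastolic pressure and heart rate. No numerical limits are suggested here, because the documents give none.
2. Tabulate the number and percentage of subjects whose worst post-baseline value meets the criterion and, separately, those whose worst change does. State that unscheduled ECGs, which protocol 9.3.3.3.3 calls for after cardiac-related adverse events, are included.
3. Present the counts for Rollover AXS-05, Rollover Placebo and Direct Entry (SAP 7.2) and overall, with a note on baseline. SAP 7.3 takes the last measurement on or before enrollment. Protocol 9.1.1 allows Day 1 to be combined with the final visit of Study AXS-05-TRD-201, and the schedule of assessments marks the Visit 1 ECG and vital signs as done there. Rollover AXS-05 baselines may therefore follow earlier AXS-05 exposure, so change-based counts in that group and overall may understate drug-related change. Counts based on the value itself do not use the baseline.

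The cost is about two added tables from data already collected, with no new visits or procedures.

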10.5. Vital Signs

Descriptive summaries (mean, SD, median, minimum, and maximum) of actual values and changes from baseline will be calculated for systolic blood pressure, diastolic blood pressure, heart rate, respiratory rate, oral body temperature, and weight. Changes in weight will be further presented by the percentage of subjects with a 7-10%, >10% to 15%, and $\geq 15\%$ weight change from baseline over time.

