##### Phase 2 Trial of AXS-05 in MDD (Study AXS-05-MDD-201)

Study AXS-05-MDD-201, was a Phase 2 randomized, double-blind, active-controlled, multi-center, trial in which 80 adult subjects with a diagnosis of moderate to severe MDD, confirmed by an independent clinical assessor, were treated either with AXS-05 (45 mg DM HBr / 105 mg bupropion HCl) (n=43), or the active comparator bupropion (105 mg) (n=37), twice daily for 6 weeks. The primary endpoint of the study was the change from baseline in the Montgomery

Åsberg Depression Rating Scale (MADRS) total score, calculated at each time point in the study and averaged (overall treatment effect).

Treatment with AXS-05 resulted in a substantial, rapid, and statistically significant reduction in depressive symptoms as compared to the active comparator bupropion. On the primary endpoint, AXS-05 was associated with a statistically significant average mean reduction from baseline in the MADRS total score over the 6-week treatment period of 13.7 points for AXS-05 compared to 8.8 for bupropion ( $p<0.001$ ). At Week 6, AXS-05 was associated with a mean reduction from baseline in the MADRS total score of 17.2 points compared to a reduction of 12.1 points for bupropion ( $p=0.013$ ). Remission, prospectively defined as a MADRS total score of  $\leq 10$ , was seen at Week 6 in 47% of patients who received AXS-05, compared to 16% of patients who received bupropion ( $p=0.004$ ). AXS-05 was superior to bupropion on multiple other prespecified secondary endpoints, with statistically significant effects demonstrated on most, including the MADRS-6, Clinical Global Impression of Improvement (CGI-I), and Clinical Global Impression of Severity (CGI-S).

AXS-05 was safe and well tolerated with no reported serious adverse events (SAEs). The most commonly reported AEs in the AXS-05 arm were nausea, dizziness, dry mouth, decreased appetite, and anxiety. Overall, rates of AEs were similar between AXS-05 and bupropion. There was no meaningful difference between the two treatment arms in discontinuations due to AEs. Treatment with AXS-05 was not associated with psychotomimetic effects, weight gain, or sexual dysfunction.

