### **12.4.5. Vital Signs**

Descriptive summaries (mean, SD, median, minimum, and maximum) of actual values and changes from Baseline will be calculated for systolic blood pressure, diastolic blood pressure, heart rate, respiratory rate, oral body temperature, and weight.

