7. DEFINITIONS AND CONVENTIONS

7.1. General Considerations

Continuous data will be summarized using descriptive statistics: number of observations (n), mean, standard deviation (SD), median, minimum, and maximum. Frequencies and percentages will be used to summarize categorical (discrete) data. Presentations of categorical data will generally suppress percentages for items where the count is zero in order to draw attention to the nonzero counts. In general, mean, standard deviation (SD), median, minimum, maximum, and percentages will be presented with one decimal.

Data listings will present all data collected on case report forms (CRFs) by group, center, and subject number.

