- Percentage of subjects achieving remission on both the MADRS and SDS (MADRS total score ≤ 10 and SDS total score ≤ 6) over time

Unless otherwise stated, the changes will be derived in such a manner so that a positive change is indicative of improvement. For example, since the higher the MADRS, the greater impairment, the change for MADRS will be derived as baseline - post baseline. Change from baseline related variables will be analyzed using paired t-tests. Between treatment differences may be performed when appropriate (e.g., sufficient sample size).

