10.2. Adverse Events

Each AE and SAE term will be recorded as a verbatim term on the case report forms (CRFs). All AEs and SAEs will be coded by primary system organ class (SOC) and mapped to a preferred term using the MedDRA dictionary Version 22. The investigator will assess AE severity and relationship to the study treatment.

All AEs will be listed. However, only treatment emergent adverse events (TEAEs) will be included in the AE summaries. A TEAE is defined as any AE with an onset date in the interval between the first study treatment dosing date and 7 days after the last study treatment dosing date. In addition, any AEs occurring after the first dose that the investigators deem to be treatment related will also be considered TEAEs and will be included in the AE summaries.

For the purpose of calculating treatment emergence and inclusion in summary tables, incomplete onset dates will be imputed using the method described in [Appendix 1](#).

AEs will be summarized by the number and percentage of subjects in each primary SOC and preferred term. Subjects will be counted only once for each primary SOC and each preferred term. Summary tables of AEs by primary SOC, preferred term and severity will be provided. If a subject has more than one AE coded to the same preferred term, the subject will be counted only once for that preferred term by using the event with the highest severity. Similarly, if a subject has more than one AE within a primary SOC category, the subject will be counted only once in that SOC category by using the event with the highest severity. AEs by primary SOC, preferred term and relationship to study drug will be provided as well. In addition, serious adverse events (SAEs) by primary SOC and preferred term will be provided. Deaths and SAEs will be summarized similarly to AEs. All adverse event tables will also include the total number of events, counting multiple events per Subject.

In the AE summary, preferred terms within each SOC will appear in frequency order.

Frequencies for deaths and hospitalizations will also be summarized by treatment group and overall.

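### The SAP's weight-change bands do not separate gain from loss, and exactly 15% falls in two of them; two scale ranges also need small corrections

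*SAP*

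**What the plan says.** SAP 10.5 plans two summaries of weight. The first is general: "Descriptive summaries (mean, SD, median, minimum, and maximum) of actual values and changes from baseline" for each vital sign, weight included. The second is a set of bands specific to weight: "Changes in weight will be further presented by the percentage of subjects with a 7-10%, >10% to 15"%. The end of that sentence gives the upper two bands as ">10% to 15%, and $\geq 15\%$ weight change from baseline over time". Gain, loss, signed and absolute are not mentioned.

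Protocol 12.4.5 plans only the general summary ("Descriptive summaries (mean, SD, median, minimum, and maximum) of actual values and changes from Baseline will be calculated for systolic blood pressure" and the other vital signs) and has no bands. The SAP's one sign rule is in the efficacy section, 9.1: "Unless otherwise stated, the changes will be derived in such a manner so that a positive change is indicative of improvement". Neither document says which direction of weight change would be an improvement.

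On the two scales, SAP 6.1.6 and protocol 9.3.1.4 score each Q-LES-Q-SF item from 0 to 5 and give the sum of 14 items as 14 to 70. The SAP adds that the transformed score runs from 0% to 100%. SAP 6.1.3 gives the five-item MADRS-5 a range of 0 to 25, while SAP 6.1.1 scores each MADRS item from 0 to 6.

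**The concern.** Long-term safety is the study's primary objective, and treatment lasts up to 15 months. The bands are the only planned count of subjects who pass a weight threshold. A large gain and a large loss are different safety findings, and a table that adds them together cannot tell the reader which occurred. Because the direction is left open, two programmers could also build different tables from the same sentence. The double inclusion of 15% lets one subject be counted twice, so the rows need not add up.

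The scale ranges are a separate matter. They are internal inconsistencies in the descriptions of efficacy instruments, and the question is whether they change any result.

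**Working it through.** **1. Bands applied as written (SAP 10.5).** Each test value is placed in the bands under two readings: change in either direction (absolute), and positive change only (signed).

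| Change | Absolute reading | Signed reading |
|---|---|---|
| +8% | 7-10% | 7-10% |
| -8% | 7-10% | no row |
| +15% | >10% to 15% and ≥15% | >10% to 15% and ≥15% |
| -20% | ≥15% | no row |
| +20% | ≥15% | ≥15% |

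**2. Pooling.** Take N = 150 (the planned enrolment, used only as an illustration) and assume 12 subjects with a change of 15% or more. The absolute cell is 12/150 = 8.0% for every mix. Behind it, gains are 8.0%, 4.0% or 0.0% when the split is 12 and 0, 6 and 6, or 0 and 12.

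**3. Can the other weight statistics recover the split?** Assume 150 subjects, all 80 kg at baseline, so 12% = 9.6 kg and 2% = 1.6 kg.
- Set A: 15 at +9.6 kg, 5 at -9.6, 60 at -1.6, 70 unchanged.
- Set B, the mirror image: 5 at +9.6 kg, 15 at -9.6, 60 at +1.6, 70 unchanged.
- Mean: A = (15×9.6 - 5×9.6 - 60×1.6)/150 = (144 - 48 - 96)/150 = 0; B = 0.
- SD, both: √[(20×9.6² + 60×1.6²)/149] = √(1996.8/149) = 3.66 kg.
- Median, both: 0. In A, 65 are below zero, 70 at zero and 15 above; B is the reverse.
- Minimum and maximum, both: -9.6 and +9.6 kg.
- Unsigned >10% to 15% band, both: 20/150 = 13.3%.

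Every planned weight summary agrees, yet large gains are 15/150 = 10.0% in A and 5/150 = 3.3% in B, and large losses are the reverse. The sets were built to match. They show that the split can be lost, not how often or by how much it would be.

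**4. Overlap at 15%.** If weight is recorded to 0.1 kg (an assumption), an exact 15% change needs 0.15×W to be a multiple of 0.1 kg, so W must be a multiple of 2.0 kg. From 50.0 to 120.0 kg that is 36 of 701 possible baselines, or 5.1%. This is the share of baselines at which the event is possible, not its frequency; the subject must also change by exactly that amount.

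**5. Q-LES-Q-SF (SAP 6.1.6).** Total range = 14 × item minimum to 14 × item maximum; percent = (raw - 14)/(70 - 14).
- Items 1-5: total 14 to 70; percent 0/56 = 0% to 56/56 = 100%. This reproduces both stated ranges.
- Items 0-5, as written: total 0 to 70; percent -14/56 = -25% to 100%. This reproduces neither.

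**6. MADRS-5.** 5 × 6 = 30, so the range is 0 to 30.

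**The case against.** The best defence is that this is a small presentation gap. Weight is not a named endpoint: the primary endpoint is TEAE incidence (protocol 12.1.1), and the vital-sign endpoint names blood pressure and heart rate (protocol 12.1.2). The bands go beyond the protocol, in an open-label descriptive study, and no decision hangs on them. Other output exists as well. The minimum and maximum would show an extreme loss or gain. For adverse events, "AEs will be summarized by the number and percentage of subjects in each primary SOC and preferred term". For individual data, "Data listings will present all data collected on case report forms (CRFs) by group, center, and subject number".

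Most of that stands, and it limits the weight of the point. It does not remove it. An extreme is not a count, the AE tables depend on an investigator reporting the weight change as an event, and a listing preserves the sign without summarising it.

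Three stronger readings are tempting, and the documents do not support them.
- A reader might infer that losses will be left out of the table. That requires taking change to mean gain. The sentence does not say so, and the ordinary meaning covers both directions; pooling is the likelier result.
- A reader might infer that the protocol's account of earlier studies flags both directions. It does not: its statements about weight concern gain only. One study's AE list includes reduced appetite ("The most commonly reported AEs in the AXS-05 arm were nausea, dizziness, dry mouth, decreased appetite, and anxiety"), but the corresponding lists for the other two studies do not, and appetite is not weight.
- A reader might infer that Q-LES-Q-SF results will be wrong. The printed minimum of 14, maximum of 70 and 0%-100% range all agree with 1-5 coding, under which nothing changes numerically.

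**Conclusion.** The point holds as a specification gap in a supplementary safety table. As written, and read in the ordinary way, the table pools gains with losses, and neither the protocol nor the rest of the SAP settles the direction; the efficacy sign rule cannot, because no improving direction is defined for weight. The planned descriptive statistics need not recover the split. How much would be hidden in this trial cannot be known from the documents: the figures above rest on assumed counts and a common baseline weight. The 15% overlap is certain on the text but rare in effect.

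The Q-LES-Q-SF item range is inconsistent with its own total and formula in both documents. It is probably a wording slip, with no effect if the CRF stores 1-5. The MADRS-5 upper limit is wrong on the SAP's own item scoring, but no listed analysis uses it, so the correction is editorial.

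**What to change.** In SAP 10.5, define the bands as 7-10%, >10% to <15% and ≥15%, and tabulate them separately for gain from baseline and loss from baseline. The cost is a few words and one extra set of rows in one table.

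As separate minor corrections:
- Q-LES-Q-SF: confirm the item coding on the CRF. If it is 1-5, change the item range to 1-5 in SAP 6.1.6 and protocol 9.3.1.4 and leave the formula as it is. Only if items are truly stored as six levels, 0-5, would the raw range, minimum and denominator need to change instead (0-70, 0 and 70). The cost is one check and one phrase in each document.
- MADRS-5: change the range in SAP 6.1.3 to 0-30. The cost is one number.

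The SAP changes can be made before the final version is documented ahead of database lock, as SAP section 2 requires.
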